Targeted Reminders

The technology being deployed has customizable reminders, however, for the present study reminder variations will be limited in order to maintain a level of consistency within the research treatment group. Patients will be thoroughly briefed on the reminder program both orally and in writing at enrollment. The reminder program is as follows:

1. Patients can opt for either text messages OR phone call reminders at the dosage time of their choosing (e.g. 9:30AM morning dose)
 - a. The TowerView system will send the patient a reminder text OR phone call at a variable time between 5-15 minutes after the dosage time of their choosing
 - b. The reminder delivered by phone will be: "Please don't forget to take your [morning, afternoon, or nightly] medication! Please press "1" if you took your medication before receiving this call or "2" if this call prompted you to take your medication. –The Penn Medicine Team"
 - c. The reminder delivered by text will be: "Please don't forget to take your [morning, afternoon, or nightly] medication! Please text "Y" if you took your medication before receiving this message or "P" if this message prompted you to take your medication. – The Penn Medicine Team."
2. The system will continue to sense if patients took their medication. 30 minutes after the first notification our software will make a determination as to whether a dose was actually taken
 - a. If the dose WAS taken no reminder is initiated until the next dose becomes due
 - b. If the dose WAS NOT taken we will reach out again with another text OR phone call reminders
 - i. The reminder delivered by phone will be: "Please don't forget to take your [morning, afternoon, or nightly] medication! Please press "1" if you took your medication before receiving this call or "2" if you'd like to be reminded again later. –The Penn Medicine Team"
 - ii. The reminder delivered by text will be: "Please don't forget to take your [morning, afternoon, or nightly] medication! Please text "Y" if you took your medication before receiving this message or "P" if this message prompted you to take your medication. –The Penn Medicine Team."
3. If a patient responds (Y or 1) or does not respond at all reminders cease until the next dose of their medication. If they respond (P or 2) the system will sense for a medication dose until 30 minutes elapse at which point it will send the following message by either text message OR phone call.

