 - a. "This is the last reminder to take your [morning, afternoon, and nightly] medication! There is no need to respond to this notification –The Penn Medicine Team"
4. All patients will receive an automated phone call reminder to refill their medication tray 10 days prior to their refill date. Patients with cell phones will also receive a text message reminder.
 - a. "Please be sure to refill your medications by calling [contact] during regular business hours"-The Penn Team"

Patients will have the option to turn on or off the pillbox's light and sound feature. The rationale for introducing the "P" or "2" option into the reminder system is to better understand if reminders before a medication dose are constructive when compared to simply reminding a patient after they have already forgotten their dose. Notifications after a dose is due may reduce reminder fatigue as the patient is given the opportunity to remember their dose from memory alone.

Research Coordinator Outreach

In addition to patient facing software through which patients can view their medication adherence and make changes to notification schedules, TowerView has designed a care coordinator/nurse dashboard. Using this dashboard the research coordinator is able to view the adherence of all patients using the connected pillbox. Patients who are continuously nonadherent- 3 consecutive missed doses or 5 doses out of 12 over a 4-day period receive targeted outreach from the research coordinator. This call is designed to explore the etiology of patient nonadherence as well as potentially change patient behavior using motivational interviewing techniques.

Primary Endpoint:

- Medication adherence as defined by PDC rates for both the treatment and control group

Secondary (Exploratory) Endpoints:

- Time to treatment discontinuation (rate of medication persistence)
- Glycated hemoglobin (HbA1C), which is generally collected every three months as part of routine clinical care for diabetic patients with HbA1C over 7.5
- Blood pressure
- Body Mass Index (BMI)
- Emergency Room (ER) visits
- Absolute cost
- Overall healthcare utilization
- Patient Satisfaction with research treatment
- Time to research coordinator outreach event
- Number of research coordinator outreach event
- Automated phone or text message reminder trends (e.g. number of reminders required)

Post Enrollment Events

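### At the second reminder, phone reply 2 and text reply P mean different things but share one branch and one rationale, which blurs the exploratory reminder data

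*Combined protocol and SAP*

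**What the plan says.** All the reminder rules are in the protocol's Targeted Reminders section. The channel is the patient's choice: "Patients can opt for either text messages OR phone call reminders at the dosage time of their choosing".

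- **First reminder.** On the phone (step 1b), 2 is to be pressed "if this call prompted you to take your medication". By text (step 1c), P is to be sent "if this message prompted you to take your medication". The two codes agree.
- **Second reminder**, sent if the system judges 30 minutes later that the dose was not taken. On the phone (step 2b(i)), 2 is now to be pressed "if you'd like to be reminded again later". By text (step 2b(ii)), P is still defined by the words "if this message prompted you to take your medication".
- **Step 3.** "If a patient responds (Y or 1) or does not respond at all reminders cease until the next dose of their medication". For the other replies: "If they respond (P or 2) the system will sense for a medication dose until 30 minutes elapse", and then the last reminder is sent.

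The section opens by saying that "reminder variations will be limited in order to maintain a level of consistency within the research treatment group". It closes with a single rationale for the P or 2 option: to learn whether a reminder before the dose helps, compared with one sent after the patient has forgotten.

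The data feed one item under Secondary (Exploratory) Endpoints: "Automated phone or text message reminder trends (e.g. number of reminders required"). Post Study Analysis lists text and phone trends again, to be analysed if the sample size permits. Neither place gives a coding or analysis rule for the replies.

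**The concern.** A reply code is useful only if it has one meaning. Here the phone 2 changes meaning between two calls about the same dose, and at the second reminder it no longer matches the text code with which step 3 groups it. One reply says that the reminder worked; the other asks for a further reminder.

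Two things are at stake. The first is the stated purpose of the code, which is to learn whether reminders prompt doses. A second-call 2 carries no such information. The second is the count of reminders needed per dose. The reply decides whether a third message goes out, so the count can differ between channels for reasons unrelated to adherence. Because patients choose their channel, such a difference would also be mixed with whatever distinguishes patients who prefer texts from those who prefer calls.

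**Working it through.** The check is a comparison of wording. I read step 3 as governing replies to the second reminder. If it also governed the first, silence there would end reminders, and that would conflict with step 2b.

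**Meaning of the codes**

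| Reminder | Phone 2 | Text P |
|---|---|---|
| First (1b, 1c) | prompted by this reminder | prompted by this reminder |
| Second (2b(i), 2b(ii)) | wants a later reminder | prompted by this reminder |
| Action under step 3 | sense for 30 minutes, then last reminder | the same |

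**What a patient can truthfully answer at the second reminder**

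| Patient's true state | Phone | Text |
|---|---|---|
| Took the dose before the message | 1, reminders stop | Y, reminders stop |
| Prompted by the message | no matching code | P, goes to the last-reminder branch |
| Not taken, wants another reminder | 2, goes to the last-reminder branch | no matching label; only P leads there |
| Does not reply | reminders stop | reminders stop |

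The first and last rows agree across channels. The two middle rows do not, and each channel lacks a label that the other has. The P-or-2 branch can therefore hold prompted text users, text users who chose P only to get another reminder, and phone users asking for another reminder.

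**Effect on the reminder count.** At most three messages can be sent for a dose (first, second, last), and the reply to the second decides only whether the last is sent. The largest possible shift is 3 − 2 = 1 reminder per dose. Whether a prompted text user actually gets that third message depends on a point that step 3 leaves open:

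- If a dose sensed within the 30 minutes cancels the last message, a text user who replied P and took the dose has a count of 2.
- If it does not cancel it, the same patient has a count of 3. A prompted phone user who pressed 1 or stayed silent has 2.

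For a patient who wants another reminder and takes no dose in the interval, the phone count is 3. The text count is 3 if the patient replies P and 2 if the patient stays silent because no label fits.

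**Effect on the primary analysis.** Under Measuring Adherence, PDC is calculated from pharmacy benefit data, and under Statistical Analysis the change in PDC is compared between randomized arms. Neither uses a reply code. The sample size does not depend on the codes either, and it reproduces: n = 2 × (1.960 + 0.842)² × (30/15)² = 62.8, so 63 per arm; 63/0.85 = 74.1, so 75 per arm, as stated.

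**The case against.** The strongest answer is that this is a drafting slip between two scripts, with very little resting on it. Much of that stands.

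- A reader might infer that text and phone users receive different interventions. The documents do not support that. Message timing, dose sensing, the first-reminder codes, the action after P or 2, and the last message are common to both channels. The consistency aim is also one of degree: patients may choose the channel and dose times, and may switch light and sound on or off. What differs is the reply option at the second reminder and how the patient reaches the third.
- A reader might infer that text users cannot get the last reminder. They can, because a text P leads to it. The option is mislabelled for that purpose, not absent. Patients are also to be briefed orally and in writing at enrollment. The content of that briefing is not given, so it may or may not explain the code.
- A reader might infer that the replies will be wrongly pooled. No section says so, and no share of prompted replies is defined. The only example given for the trend endpoint is a count of messages.
- One shared branch can be defended as an operating rule, because both P and 2 imply that the dose had not been taken before the message arrived.

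This does not remove the point. The scripts are the words patients will act on, so the mismatch is more than clerical. The shared branch may be workable, but the shared rationale does not fit the second-call 2. Because step 3 and the rationale both name P and 2 together, an analyst could easily combine them.

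**Conclusion.** The point holds as a minor one. At the second reminder the phone 2 and the text P carry different meanings, yet step 3 and the rationale treat them as one. As written, phone users cannot report having been prompted by the second call, text users obtain the last reminder only under a label that says they were prompted, and 2 changes meaning between calls.

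The reach is limited to the exploratory reminder data in the treatment arm: the purpose of the code directly, and the reminder count indirectly, by at most one per dose. The number of replies affected cannot be given, because the documents report neither the channel mix nor reply rates. If both channels are in use, any combined tally of second-reminder P and 2 would mix two meanings, whatever the split.

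A reader might go further and doubt the main result. That is not supported, because the primary PDC comparison rests on pharmacy data and randomized assignment. The conclusion assumes that the scripts are run as printed and that step 3 applies to replies to the second reminder.

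**What to change.** Reconcile steps 2b(i), 2b(ii) and 3 with the rationale at the end of Targeted Reminders, so that each reply code has one meaning across both channels and both messages. This review does not say which script is right. In the same edit, state whether a dose sensed during the 30 minutes cancels the last message.

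Add one rule to Post Study Analysis: store and summarise replies by channel and by reminder number. If the scripts stay different, do not combine second-message P with 2, and report reminder counts separately for text and phone users.

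The cost is a script and software text edit before launch and one coding rule. The script edit cannot be replaced by analysis afterwards: separating the channels keeps unlike replies apart, but it cannot recover a prompted answer that phone users were never offered.

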We propose a randomized control clinical trial. Random number generation will be used to randomize patients to either the treatment group (connected pillbox) or control group (usual care). The patient will only be randomized after he or she has been briefed on the intervention and consented to participating. In this way both patients in the treatment and control groups will receive the same education regarding adherence so as to not bias the study. Patients in both the research treatment and control group will be compensated equally for their participation in the study.

Study Intervention

The study intervention is multi-modal and consists of 1) prefilled medication trays that are shipped to patient's home 2) a connected pillbox that senses when doses are missed and can initiate phone call or text reminders and 3) research coordinator outreach triggered by nonadherence. A detailed overview of each component of the intervention is presented below:

Prefilled Medication Trays

The study sponsor, TowerView Health, has developed plastic trays designed to hold all the medications in a patient's regime. Each tray has 21 medication compartments- 3 compartments (morning, afternoon, nightly meds) for each day of the week. Patients in the research intervention will receive monthly shipments of 5 prefilled medication trays from Friendship Pharmacy, Inc., an IBC participating long-term care and retail pharmacy, located at [name].

After consenting to participate in the study, the patient or patient's caregiver will provide the research coordinator with a complete list of pharmacies used by the patient. This information will be shared with the Friendship Pharmacy pharmacist who will initiate the transfer of all scripts from patient's existing pharmacy to Friendship Pharmacy. A nurse practitioner or physician at Penn Medicine will initiate any scripts that need to be rewritten. In instances where prior authorization is required or a script is denied at adjudication the Friendship pharmacist will reach out to the physician or nurse practitioner to receive authorization or make an appropriate medication change.

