A pharmacist at Friendship Pharmacy will load a patient's complete medication schedule and seal each medication tray using a heat-sealing system that uses compressed air. The system will seal each individual medication compartment in order to minimize drug waste in instances when the patient drops the pillbox or tray. Each medication compartment will be labeled with all the drug names and respective doses housed within it for quality and safety purposes. Complete printed labels identical to those found on the exterior usual care medication vials will accompany the trays in order to comply with Pennsylvania state pharmacy regulations. PRN (e.g. opioids) and frequently titratable medications (e.g. warfarin, tacrolimus) will not be included in the tray and will be provided to the patient in usual care medication vials.

Friendship Pharmacy will refill medication trays on a monthly basis only at patient request. An automated reminder will be initiated 10 days prior to the patients refill date. Failure to refill will be followed up by a personalized call from Friendship Pharmacy 7 days prior to the patients expected refill date. Refill reminders will continue every 3 days after initial outreach until patients initiate a tray refill.

Connected Pillbox

After consenting to participate in the study patients will receive a connected pillbox that has been activated for use on the Verizon Wireless network. Using embedded sensors, the pillbox senses volume changes within individual compartments and sends this raw, encrypted data to a dedicated server in the cloud. TowerView's algorithms process capacitance data and determine whether a patient took his or her medications. In instances when patients did not take their medications, TowerView can send the patient an automated text message, phone call, or email reminder. For patients who prefer not to receive such notifications the pillbox comes equipped with visual (flashing blue light) and audio (loud beeping) reminders as well.

Initial notification schedules will be assigned based on patient preference by the research coordinator (ex: 9AM, 3PM, 9PM). Using TowerView's web based software, however, patients can alter their notification

schedule at any time; furthermore, notifications can be set for medications that do not reside within the pre-filled trays. This feature has been added to accommodate PRN, frequently titratable and injectable medications that are unable to be included as part of the tray.

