Patients will be consented by a trained research coordinator and have the following information collected from them:

- Electronic mailing address and phone number
- Blood pressure-once at the beginning and once at the end of the visit
- Demographic survey
- Montreal Cognitive Assessment (MoCA exam)- a screen for cognitive impairment
- Cumulative Illness Rating Scale (CIRS)- a measure of comorbid illness burden
- Short Form 12 (SF-12)- a measure of general quality of life
- Brief Medication Question (BMQ)- a self reported assessment of medication adherence and medication adherence related factors (e.g. cost burden of drugs)

Concluding Visit

Patients will return their connected pillbox and have the following information collected from them:

- Blood pressure- once at the beginning and once at the end of the visit
- HbA1c test and lipid panel if data cannot be abstracted from the chart
- Patient satisfaction and attitudes toward adherence system

The care coordinator will also assist the patient in transitioning from the tray to another method of receiving their medications. Patients will have the option of either remaining with Friendship Pharmacy or be transferred back to their original pharmacy.

Methods

Measuring Adherence

Proportion of Days Covered (PDC) is the metric currently used by CMS and NCQA to assess patient medication adherence; the metric is calculated using pharmacy benefit data. The present study utilizes an interval-based PDC calculation defined as medication possession during the interval from the index date (the patient's study start date) to the end of the period being assessed (the patient's end date). In this way, the number of days of medication supplied throughout the period becomes the numerator and is divided by the number of days in the overall period itself. Intervals during which patients are hospitalized or in hospice are excluded from the PDC calculation

As PDC is an assessment of medication adherence for a single drug the calculation must be modified for patients taking multiple medications. Of interest in this study is patient adherence to oral hypoglycemic drugs. Our group recognizes the following categories as oral hypoglycemic agents: sulfonylurea, metformin hydrochloride, glitazones, acarbose, and meglitinides.

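### The primary endpoint is named PDC, but its written formula counts days supplied, with no overlap, cap or starting-supply rule, and the resulting error need not cancel between arms

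*Combined protocol and SAP*

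**What the plan says.** The Primary Endpoint section reads: "Medication adherence as defined by PDC rates for both the treatment and control group". Under Methods, Measuring Adherence, the plan says that PDC is the metric CMS and NCQA use. It then describes the study's own interval-based version, "defined as medication possession during the interval from the index date" (the patient's study start) "to the end of the period being assessed" (the patient's end date). The operative sentence follows: "the number of days of medication supplied throughout the period becomes the numerator", divided by the days in the period.

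Two adjustments are stated: hospital and hospice intervals are excluded, and patients on several hypoglycemic drugs get the average of their per-drug values. That average also serves the below-80% eligibility test and the 9-month pre-study value in the change score.

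Supply arrangements differ by arm. Under Prefilled Medication Trays, the new pharmacy's pharmacist is the one "who will initiate the transfer of all scripts" for treatment patients. On refills: "An automated reminder will be initiated 10 days prior to the patients refill date", then a personal call at 7 days, and "Refill reminders will continue every 3 days after initial outreach until patients initiate a tray refill". Refills are made only when the patient asks. Post Enrollment Events ties the trays to a 30-day reimbursed fill and leaves controls with their existing pharmacy.

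**The concern.** Days supplied are not the same as days covered. Two fills that overlap add their full length to the numerator although each calendar day can be covered only once. A fill late in follow-up may count days after the end date. Supply already at home on the start date counts for nothing. The plan has no rule for overlap, for a per-drug cap or for starting supply.

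Randomization balances errors in the pre-study value in expectation. It does not protect the follow-up value, because the intervention itself changes when and how treatment patients fill. The missing rules therefore concern the very thing that differs between arms. Two analysts following the same section could report different primary results, and one who settles the rules after seeing the claims could move the estimate.

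**Working it through.** **Yardstick.** Target Population and Statistical Analysis give a 15-point difference, SD 30, 80% power, two-sided 0.05 and 15% dropout. Per arm, 2 × (1.960 + 0.842)² × (30/15)² = 62.8, so 63; 63/0.85 = 74.1, so 75. The plan's 75 per arm is reproduced. None of these inputs depends on how days are counted.

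**Inputs for the illustrations.** From the documents: 30-day tray fills, 6 months of follow-up (taken as 180 days), reminders from 10 days ahead. Assumed: all fill dates, the day of the first tray, and the share of earlier days covered by old supply. The monthly five trays are counted as 30 days' supply, since the plan ties them to a 30-day fill.

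**1. One patient, refilling 10 days before every run-out.** Fills fall on days 0, 20, 50, 80, 110, 140 and 170.
- Written formula: 7 × 30/180 = 210/180 = 116.7%.
- End-date cut only: (6 × 30 + 10)/180 = 190/180 = 105.6%.
- Distinct days: 180/180 = 100%, which is the true coverage.
- If the fills come exactly on time (days 0, 30, ..., 150), the formula gives 180/180 = 100% and there is no error.

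**2. Mean over tray patients refilling 0 to 10 days early.** Let the first tray come on day s, uniform on 0–14 or 0–21, with each later refill L days before run-out, L uniform on 0–10. Fills fall on day s and on days s + 30k − L. Six always fall before day 180. The seventh, on day s + 180 − L, counts when L > s, with probability 5/14 = 0.357 or 5/21 = 0.238. Let h be the share of days before the first tray that old supply covers.
- Written mean: (180 + 30 × probability)/180.
- True mean: 1 − (1 − h) × mean(s)/180, with mean(s) = 7 or 10.5.
- End-date cut only: counted days are 180 + L − s, mean 178 or 174.5.

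| First tray | h | Written | True | Excess | Excess with end-date cut only |
|---|---|---|---|---|---|
| 0–14 | 0 | 106.0% | 96.1% | +9.8 | +2.8 |
| 0–21 | 0 | 104.0% | 94.2% | +9.8 | +2.8 |
| 0–14 | 0.65 | 106.0% | 98.6% | +7.3 | +0.3 |
| 0–21 | 0.65 | 104.0% | 98.0% | +6.0 | −1.0 |

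With 183 days the excess runs from 6.6 to 11.5. The negative entry arises because starting supply is not credited. Distinct-day counting with starting supply credited has no error in this pattern.

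**3. What shrinks it.** If claims are dated at run-out (L = 0), the written mean is 100% and the excess is 100 − 98.6 = 1.4 to 100 − 94.2 = 5.8 points. If only 25–50% of tray patients refill early, the arm mean moves by about 0.25 × 6 = 1.5 to 0.5 × 10 = 5 points. These are errors in one arm's mean, not in the arm difference.

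**4. Why the sign is open.** Suppose fills are 90 days, which the documents do not mention. Fills on days 0 and 120 score 180/180 = 100% for true (90 + 60)/180 = 83.3%. Fills on days −5 and 95 score 90/180 = 50% for true (85 + 85)/180 = 94.4%.

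**5. Left-over vials.** A renewal simulation (assumed earlier coverage 30–80% or 50–80%, refill habits unchanged, first tray on days 0–21) gives these errors in the arm difference, in points:

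| Earlier fills; old vials | Written | Distinct days, shifted forward | Distinct days, stopped at first tray |
|---|---|---|---|
| 30-day; set aside | +4.4 to +6.4 | +4.4 to +5.5 | 0 |
| 30-day; used first | −0.3 to +0.6 | 0 | −4.4 to −5.6 |
| 90-day; set aside | +4.1 to +6.6 | +10.6 to +13.5 | 0 |
| 90-day; used first | −8.3 to −11.3 | 0 | −13.4 to −16.4 |

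**6. Eligibility.** Drug A with 10 fills of 30 days in 270 days scores 300/270 = 111.1%. With drug B at 50%, the mean is 80.6% uncapped (excluded) but (100 + 50)/2 = 75% capped (eligible).

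**The case against.** The strongest defense is that the section names a standard metric, refers to CMS and NCQA, and limits possession to the study interval, so the supply sentence may be loose shorthand. That has some force: an end-date cut can fairly be read into the text, and nothing proves that the analysis will be run as a raw ratio. But the sentence is the only formula given, and an end-date cut settles neither overlap nor starting supply.

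It is also fair that a reminder is not a claim. Refills are at the patient's request, no passage says a claim is dated when the reminder goes out, and the plan foresees cases where "a script is denied at adjudication", which might block some early fills. The 116.7% patient refills early every time, in a population chosen for adherence below 80%. These points reduce the likely size but do not supply the missing rule.

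Two stronger readings are tempting:
- **A reader might infer a false-positive rate of 17–23%.** At 75 per arm and SD 30, a bias of +5 to +6 points would do that. In the calculations above, however, an arm-difference bias of that size comes from old vials being set aside. With 30-day earlier fills, counting distinct days and shifting supply forward leaves it almost unchanged (+4.4 to +5.5), so it cannot be charged to the written numerator.
- **A reader might infer that most of a 15-point effect could be hidden, with power falling from 86% to 17%.** That requires 90-day earlier fills and old vials finished before the trays. The documents mention no 90-day fills, and a pillbox left untouched for weeks would register missed doses and prompt coordinator outreach.

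The eligibility example precedes randomization, so it affects who enrolls and does not bias the arm comparison.

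**Conclusion.** The concern holds as a defect in the endpoint definition that should be corrected before analysis. Taken literally, the formula is a possession ratio that can exceed 100%, and the missing rules bear on fill behavior that the intervention changes in one arm only.

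The net effect on the arm difference cannot be sized or signed from the documents. The illustrated excess of roughly 6 to 10 points in the treatment mean rests on assumed fill dates and early refilling by every tray patient. It falls to about 1.5 to 5 points if a quarter to a half of them do so, and also falls if claims come nearer run-out. An end-date cut alone removes most of it but not all. The documents do not support a claim that the trial is biased in a known direction, or that its error rate or power is changed by a known amount.

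**What to change.** In Measuring Adherence, replace the numerator with the number of distinct days in the interval on which each drug is on hand. Shift overlapping supply forward, cut supply at the patient's end date, and cap each drug at 100% before averaging. Apply this identically in both arms and to the 9-month baseline and eligibility values.

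For pre-index supply, name one rule in advance for the p < 0.05 test: either carried in and shifted forward, or stopped at the first tray fill. Report the other as a sensitivity analysis. State that claims cannot show whether old vials were used, so neither rule removes that uncertainty, and that with long earlier fills either can err by more than the written formula.

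The cost is one paragraph of SAP wording and a little claims programming. Carrying supply into the 9-month baseline needs claims from one fill length earlier. Sample size does not change. If earlier fills were long, the two results may lie far apart.
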